## MRI Analysis

### *Lesion activity:*

The CE gadolinium and USPIO lesion number and lesion volume (LV) were measured on T1 post-contrast images, respectively, using a semi-automated edge detection contouring/thresholding technique previously described. Unenhanced T1 images were always used for comparison, and USPIO and gadolinium CE lesions were judged together as they would theoretically be in clinical situations. The cumulative number of CE gadolinium and USPIO lesions were obtained by summing the total number of these lesions between baseline to 6, 6 to 12, 12 to 24 months and 24 to 36 months.

The T2 new/enlarging lesions were assessed on FLAIR sequence. Using FMRIB's FLIRT, all follow-up FLAIR and T1-SE post-contrast images for a given subject were co-registered to its baseline FLAIR image using a 6 degrees-of-freedom rigid-body model. All subsequent lesion analyses were done using the co-registered images. For each time point, T2 lesion activity analysis was performed via the aid of a "subtraction image." Briefly, the image from the previous time point was subtracted from the corresponding current image. The result was then be smoothed with a Gaussian kernel of 0.5 mm. Cross-sectional regions of interest was overlaid on the subtraction image to facilitate the identification of new and enlarging T2 lesions. T2 and T1-LCs was calculated using JIM software (version 6.0, Xinapse Systems, Northants, UK, <http://www.xinapse.com>).

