### **Revision History**

Revision #	Version Date	Summary of Changes	Consent Change?
1	24/06/2021	Change based on the new study protocol	Yes
2	28/02/22	Addition of Dent Institute as a recruitment and testing site	New MS consent for DENT; Yes to current MS consent form

PROTOCOL TITLE: Open-label, single-blinded, observational, prospective, 36-month, longitudinal, controlled study to assess the efficacy of siponimod (Mayzent®) on microglia in patients with secondary progressive forms of multiple sclerosis

3	07/04/2022	Inclusion of 15 healthy controls to undergo 1 PET scan and 1 MRI scan.	New HC consent form
4	11/9/2022	Including Great Lakes Medical Imaging as a PET scanning site	No
5	03/03/2023	Closing enrollment and follow-up of MS patients; Closure letter; continued enrollment of HCs	Yes - HC

PROTOCOL TITLE: Open-label, single-blinded, observational, prospective, 36-month, longitudinal, controlled study to assess the efficacy of siponimod (Mayzent®) on microglia in patients with secondary progressive forms of multiple sclerosis

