## 1.0 Study Summary

Study Title	Open-label, single-blinded, observational, prospective, 36-month, longitudinal, controlled study to assess the efficacy of siponimod (Mayzent®) on microglia in patients with active secondary progressive forms of multiple sclerosis
Study Design	Open label, single-blinded, observation, prospective, longitudinal BNAC MRI analysts are blinded to subject's medication treatment.
Primary Objective	The assessment of the effect of Mayzent over at least 24 months on the evolution of microglia pathology in patients with active secondary-progressive (SP) MS.
Secondary Objective(s)	(a) compare the effect of Mayzent to the control group of active SPMS patients treated with ocrelizumab (Ocrevus®), as measured by changes in microglial activation in the lesional and non-lesional normal appearing (NA) WM and GM, and in the peri-plaque area of chronic lesions in the brain; (b) the relationship between changes in microglial activation in the lesional and non-lesional normal appearing

PROTOCOL TITLE: Open-label, single-blinded, observational, prospective, 36-month, longitudinal, controlled study to assess the efficacy of siponimod (Mayzent®) on microglia in patients with secondary progressive forms of multiple sclerosis

	
(NA) WM and GM, and in the peri-plaque area of chronic lesions in the brain and clinical and behavioral outcomes.
 
(b) to validate the quantification approach and to use as a statistical control group (15 HCs) when looking at an increase in TSPO in a parametric map of the brain

Research Intervention(s)/ Investigational Agent(s)	MRI and PET scans, clinical visits, questionnaires, eye exam, blood sampling.
IND/IDE #	
Study Population	
Individuals with active Secondary Progressive Multiple Sclerosis (SPMS)
 
Activity is determined by MRI activity (contrast-enhancing lesions; new and unequivocally enlarging T2 lesions) and/or clinical relapses in the 24 months prior to the study baseline.
 
15-age-matched healthy controls (10 females and 5 males aged between 18-65 years)

Sample Size	60 MS patients; 15 healthy controls
Study Duration for individual participants	
2-3 years: MS Patients
 
Approximately 4 hours: healthy controls – 1 timepoint

Study Specific Abbreviations/ Definitions	

AEs	Adverse Events
BBB	Blood-brain-barrier
BICAMS	Brief International Cognitive Assessment for MS
BNAC	Buffalo Neuroimaging Analysis Center

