Response: We plan to enroll 60 patients over an 18-month period. We believe this is quite feasible. Approximately 10 patients are prescribed Ocrevus and Mayzent in a month. (5 each) – *no longer applicable*

We also plan to enroll 15 healthy controls who are age and gender matched.

*8.3 Describe the time that you will devote to conducting and completing the research.*

Response: 60 months

*8.4 Describe your facilities.*

Response: BNAC is an MRI reading center located within Buffalo General Hospital; we are protected by both the hospital firewall and internal firewalls to prevent breach of data. DENT Neurologic Institute is the largest out-patient neurology practice in the United States. GLMI currently provides the radiology services for 6 hospitals and at 5 outpatient locations in and around Buffalo NY.

*8.5 Describe the availability of medical or psychological resources that subjects might need as a result of an anticipated consequences of the human research.*

Response: Subjects will always have access to their neurologists or primary care physician.

*8.6 Describe your process to ensure that all persons assisting with the research are adequately informed about the protocol, the research procedures, and their duties and functions.*

Response: The protocol will be shared with all personnel involved in recruiting, testing, and receiving, analyzing, and reporting on MRIs. BNAC has staff meetings to inform the appropriate personnel at the

PROTOCOL TITLE: Open-label, single-blinded, observational, prospective, 36-month, longitudinal, controlled study to assess the efficacy of siponimod (Mayzent®) on microglia in patients with secondary progressive forms of multiple sclerosis beginning of each study and as necessary throughout the duration of the research.

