- If they complete planned MRI scan over day one, they will be paid \$50 and if they complete both MRIs over 2 days, they will be paid \$100
- Healthy control subjects will be paid \$250 after completion of the PET and MRI scans.

The total amount MS subjects may receive for taking part at every time point visit is \$250. If the subject has to stop any procedure of the study visit early for any purpose, he/she will still receive compensation for his/her time, as above.

If MS subjects participate through all procedures in all five visits, they will be compensated in total of \$1250.

- Healthy control subjects will be paid \$250 after completion of the PET and MRI scans.

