## 11.0 Local Number of Subjects

*11.1 Indicate the total number of subjects to be accrued locally.*

Response: 60 MS (no longer applicable); 15 HCs

*11.2 If applicable, distinguish between the number of subjects who are expected to be enrolled and screened, and the number of subjects*

PROTOCOL TITLE: Open-label, single-blinded, observational, prospective, 36-month, longitudinal, controlled study to assess the efficacy of siponimod (Mayzent®) on microglia in patients with secondary progressive forms of multiple sclerosis  
*needed to complete the research procedures (i.e., numbers of subjects excluding screen failures.)*

- Response: We estimate that 90 MS patients will need to be screened in order to achieve our enrollment goal of 60. *No longer applicable*
- Healthy control subjects will be from other studies which they participated in and consented to be contacted for participation in future studies.

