**2023-09-15**

All statistical analyses were performed using SPSS version 28.0 (IBM, Armonk, NY, USA). The data distribution was determined using visual inspection of the histograms and Q-Q plots.

Categorical data was compared using chi-square test, parametric numerical data was compared using Student's t-test and non-parametric data using Mann Whitney U test. The comparisons between the groups were further adjusted for demographic and genetic differences using analysis of covariance (ANCOVA) and adjusted estimated means were shown as mean (standard error).

Due to the small sample size and non-parametric nature of the data, the correlations were performed using non-parametric Spearman's test. Pair-wise comparisons within the subjects were also performed. P-values lower than 0.05 were considered statistically significant. Due to the exploratory nature of the study, corrections for multiple comparisons were omitted. The data was additionally visualized using box and scatter plots.

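### Read as one total per patient, the cumulative gadolinium/USPIO lesion number makes no allowance for how many follow-up scans the patient had

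*Combined protocol and SAP*

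**What the plan says.** **The count.** Under MRI Analysis, Lesion activity, the SAP says the cumulative number was "obtained by summing the total number of these lesions between baseline to 6, 6 to 12, 12 to 24 months", and the sentence goes on to the interval from 24 to 36 months. It gives no denominator, no minimum number of scans and no rule for an interval without a scan.

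**The tests.** The SAP's statistical section lists chi-square, t-test, Mann-Whitney, Spearman and within-subject comparisons. On adjustment it says "The comparisons between the groups were further adjusted for demographic and genetic differences using analysis of covariance (ANCOVA"). No term for number of scans or length of follow-up appears. Spearman was chosen "Due to the small sample size and non-parametric nature of the data".

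**Follow-up.**
- Local Supplement 1.0 gives study duration as "2-3 years: MS Patients".
- Section 10.5 refers to payment "If MS subjects participate through all procedures in all five visits", which fits a baseline and four follow-ups.
- Section 4.1 says a withdrawn patient has no further assessments. For a patient who stops medication for medical reasons, it says an End of Treatment schedule will be attempted.
- Revision 5 in the Revision History (03/03/2023) reads "Closing enrollment and follow-up of MS patients". The SAP is dated 2023-09-15, after that closure, and still describes a sum to month 36.

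**The concern.** A sum over scans grows with the number of scans. Two patients with the same lesion activity will have different expected totals if one was scanned four times after baseline and the other twice. The total then measures length of observation as well as disease activity. That weakens any description of the total, and any Spearman correlation with it. If one drug group had systematically shorter follow-up, that group would also appear to have fewer lesions. Treatment was chosen in routine care (Local Supplement 2.1), so nothing in the design guarantees equal follow-up between the groups.

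**Working it through.** The plan states no figure for this outcome, so there is nothing to reproduce.

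**1. Follow-up scans reachable.** With scans at 6, 12, 24 and 36 months, follow-up of 6 months gives 1 scan, 12 to under 24 months gives 2, 24 months gives 3 and 36 months gives 4. The planned two to three years therefore allows 3 or 4 even for a patient who completes. The second recruiting site was added on 28/02/2022. From then to 03/03/2023 is 368 days, or 12.1 months. If scanning stopped on that date (an assumption), anyone enrolled after the site was added could have at most two follow-up scans.

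**2. Effect on the expected total.** At a constant rate per scan, the expected total is rate × scans.

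| Follow-up scans | Baseline excluded | Baseline counted |
|---|---|---|
| 3 of 4 | 3/4 = 0.75 | 4/5 = 0.80 |
| 2 of 4 | 2/4 = 0.50 | 3/5 = 0.60 |
| 1 of 4 | 1/4 = 0.25 | 2/5 = 0.40 |

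The SAP does not say whether lesions on the baseline scan enter the sum.

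**3. Effect on a group comparison (illustration; all inputs assumed).** Lesion counts are gamma-Poisson with the same true rate in both groups: 0.05, 0.2, 0.5 or 2 lesions per follow-up scan, shape 0.5 or 1. Mann-Whitney is tested at two-sided 0.05, with 4,000 runs per setting and baseline excluded. Balanced means half of each group has the shorter follow-up. Unbalanced means 7 v 4 of 12, or 18 v 9 of 30, do. Entries are the range of false-positive rates over the settings.

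| Analysis | 12 per group | 30 per group |
|---|---|---|
| Raw total, balanced | 0.6–5.3% | 2.9–5.8% |
| Raw total, unbalanced, 1 v 2 scans | 0.4–5.3% | 4.6–8.5% |
| Raw total, unbalanced, 1 v 3 scans | 1.1–6.0% | 5.9–12.1% |
| Raw total, unbalanced, 2 v 3 scans | 1.3–5.4% | 4.9–6.5% |
| Raw total, unbalanced, 3 v 4 scans | 2.9–5.3% | 4.6–6.1% |
| Lesions per scan, unbalanced, all pairs | 0.4–5.8% | 4.3–6.5% |
| Common-interval sum, unbalanced, all pairs | 0.2–5.4% | 2.3–6.0% |

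Repeat runs at 30 per group put the raw-total maximum at 7.1–8.5% for 1 v 2 scans and 11.7–12.2% for 1 v 3. Counting the baseline scan lowers these maxima to about 6.3% and 8.3%. Thirty per group needs the full 60 patients split equally. Local Supplement 11.1 now gives the number as "60 MS (no longer applicable); 15 HCs".

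**4. Effect on a correlation (illustration).** With 24 patients, half with 1 scan and half with 2, and a latent correlation of 0.5, the mean Spearman coefficient is 0.24–0.39 for the raw total, 0.24–0.40 per scan and 0.21–0.38 for the common-interval sum. With 1 to 4 scans and 0.2 lesions per scan, the common-interval sum gives 0.22 against 0.27 for the raw total. The per-scan count loses nothing. The common-interval sum loses a little because it discards scans.

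**The case against.** **The reading is not settled.** The SAP lists four intervals rather than one span. The sum may therefore mean one count per interval, or the two lesion types added within an interval. If so, and if each count uses only patients scanned in that interval, the problem largely goes away. This stands, and the point is conditional on it. The word cumulative still favours a single total.

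**Unequal follow-up is inferred.** No patient's follow-up is recorded. The duration is a plan and the withdrawal text is a rule. The accrual statement, "We plan to enroll 60 patients over an 18-month period", is marked as no longer applicable, so no accrual pattern should be built on it. This also stands: unequal scan numbers are likely, not demonstrated. A reader might infer from the 20.3 months between revisions 1 and 5 (617 days) that nobody reached month 24. The documents do not support that, because they do not give the first enrolment date.

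**No analysis is shown to be harmed.** Lesion counts are not among the objectives, and the SAP does not say which outcomes are compared or correlated. A reader might infer that the siponimod–ocrelizumab comparison is biased. Simulations in which the groups differ widely in scan number (for example, everyone with 4 in one group and 2 in the other, 30 per group) do reject in about 17–50% of runs by Mann-Whitney. Nothing in the documents supports such a split, so those figures are not an estimate for this study.

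**Details may be elsewhere.** The Local Supplement accompanies a separate sponsor protocol, which may cover missed and End of Treatment scans. Their absence here is missing detail, not a demonstrated error. The SAP's own definition and covariate list still make no allowance for scan number.

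**Conclusion.** The point holds as a minor one, with medium confidence, on the one-total reading. Totals from patients with different numbers of follow-up scans are then not comparable, by a factor of up to four at a constant rate per scan (2.5 if baseline is counted: 1/0.40).

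Bias between drugs would additionally require scan completeness to differ by drug, which is not shown. With balanced follow-up the false-positive rate is essentially unaffected. The same holds at about 12 per group with roughly 60% v 30% on short follow-up. That second result covers this degree of imbalance only and would not carry over to a complete split by drug. Modest inflation appears at 30 per group with assumed imbalance, mainly when patients have 1 v 3 scans. All lesion rates, dispersions and imbalances are assumptions. The outcome is a supporting one, and the SAP describes the study as exploratory.

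**What to change.** For any comparison or correlation that uses the cumulative count:

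- **Main analysis:** lesions on follow-up scans divided by the number of follow-up scans actually read, with the SAP's Mann-Whitney or Spearman test.
- **Missing scans:** do not score an unscanned interval as zero. A patient with no follow-up scan has no rate and should be listed.
- **Reporting:** tabulate follow-up scans per patient by drug group, so that a reader can judge any imbalance.
- **Optional sensitivity analysis:** the sum over intervals that all compared patients completed.

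One added sentence should say whether the count is a single total or per interval, and how baseline and End of Treatment scans enter.

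The cost is SAP wording and one re-run on scans already read, with no new data. The per-scan count has two limits. It assumes a roughly constant lesion rate over follow-up. If the rate instead halves each interval (30 per group, 18 v 9 short), the illustrative false-positive rates are 3.7–6.0% per scan and 3.8–7.0% for the raw total. Dividing by scans also equalises the mean but not the share of zeros. With shape 1 and 0.5 lesions per scan, P(no lesions) = 1/(1 + 0.5 × scans), which is 0.50 with 2 scans and 0.33 with 4. A rank test on the rate is therefore less sensitive to scan number than one on the raw total, but not wholly free of it, and the tabulation is needed alongside it. The common-interval sum discards later scans.

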### *Brain volume analysis:*

Segmentation of deep GM structures for volumetric and QSM analysis were done using both a semi-automated edge-contouring and FMRIB's integrated registration and segmentation tool (FIRST) on 3D T1-WI. Absolute tissue volumes for the thalamus and total subcortical deep GM at each time point were estimated from inpainted 3D T1-WI images with FMRIB's Integrated

Registration and Segmentation Tool, a model-based segmentation/registration tool. Normalized volumes were obtained by multiplying the estimated volumes from this tool by the volumetric scaling factor from SIENAX and percentage volume changes were obtained between different time points. Percent thalamus volume change (PTVC) was calculated.

For baseline analyses, FMRIB's SIENAX software was used (version 2.6) with inpainted 3D T1-WI. Normalized volumes were measured.

To quantify longitudinal percentage volume changes, we used a modified hybrid of FMRIB's SIENA and SIENAX methods. We used a brain- and skull-constrained co-registration technique to place both baseline and follow-up images into a joint space halfway between the two at all time points in the study. Next, we combined baseline and follow-up intracranial volume masks via union and valid voxel masks via intersection, ensuring that the same imaging volume was analyzed at both time points. Finally, we segmented the resulting images with a modified longitudinal version of FMRIB's Automated Segmentation Tool that uses a 4-dimensional joint hidden random Markov field to prevent misclassification between time points when longitudinal intensity changes are lacking (or minimal). Total tissue volume was calculated for both baseline and follow-up for each tissue compartment from partial volume maps and percentage volume change was derived directly from the images. Percentage brain volume change (PBVC) and percentage cortical volume change (PCVC) was calculated.

#### **QSM analyses:**

QSM images were reconstructed as previously described. Magnetic susceptibility was referenced (0 ppb) to the average susceptibility of the brain, under the assumption that a larger reference region would reduce additional inter-subject variability, compared to a smaller reference region. In-house developed algorithms for QSM processing, written in MATLAB (2013b, The MathWorks, Natick, MA) was used.

#### **PET analysis:**

Prior to regional analysis, subject-specific SUV maps were created. First, list-mode data was reconstructed into 5-minute frames and then aligned in order to correct for patient motion (see Figure 6 for further details). Next, aligned, decay-corrected activity maps were combined and then converted to voxel-wise standardized uptake value (SUV) maps (Figure 7) based on injected dose (ID) and body weight (BW) at the time of injection, using the formula  $SUV = C_{img}/(ID/BW)$ . To facilitate subsequent regional analysis, SUV maps were fused with MRI using the CT scan as an anatomical proxy.

For lesional and non-lesional NAWM and NAGM, and the peri-plaque area of chronic lesions in the brain analyses, the derived regions and/or expert-traced regions of interest (ROIs) from the fused MRI were applied to the PET scans to determine lesional and non-lesional  $^{18}\text{F}$ -PBR06 binding. To correct for individual variation in tracer kinetics, SUV measures were referenced to the mean SUV of the cerebellum to produce relative SUVR measures for each relevant region of interest. Additionally, to correct for partial voluming of the larger PET voxels compared to MRI, region-based voxel-wise (RBV) correction combined with the reblurred Van-Cittert (RVC) was employed using PETPVC.
